3.2. Study Design Overview

Figure 1: Study Design Overview

Light grey highlighted visits indicate visits with ocriplasmin/ sham injection.

^a All subjects assigned to the ocriplasmin arms will receive an intravitreal injection of ocriplasmin 0.0625mg or 0.125mg at Day 0. These subjects will be re-treated with the same dose of ocriplasmin at Day 35 and at Day 70 if, by that time, they have not achieved total PVD on both B-scan ultrasound and SD-OCT, as assessed by the masked B-scan expert reader and the masked CRC, respectively. Subjects who have total PVD on both B-scan ultrasound and SD-OCT will receive subsequent sham injection(s) in place of ocriplasmin injection(s).

^b Subjects assigned to the sham arm will receive 3 sham injections at Day 0, Day 35 and Day 70.

* The masked Investigator / designee will make a **scripted phone call** to each subject 24-72 hours after the injection visit. Based on this phone call, the subject may be invited back for an unscheduled study visit, as per the masked Investigator's clinical judgement.

- **Study design.** Multi-centre, randomised, sham-controlled, double-masked, Phase 2 clinical study with 3 parallel treatment arms
- **Study arms and treatments.**
 - **Ocriplasmin 0.0625mg arm.** Approximately 46 subjects will receive up to 3 intravitreal injections of ocriplasmin 0.0625mg, approximately 1 month apart. All subjects assigned to this arm will receive an intravitreal injection of ocriplasmin 0.0625mg at Day 0. These subjects will be re-treated with ocriplasmin 0.0625mg at Day 35 and at Day 70 if, by that time, they have not achieved total PVD on both B-scan ultrasound and SD-OCT, as assessed by the masked B-scan expert reader and the masked CRC, respectively. Subjects who have total PVD on both B-scan ultrasound and SD-OCT will receive subsequent sham injection(s) in place of ocriplasmin injection(s).

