6. TREATMENT OF SUBJECTS

6.1. Description of Study Drugs

Table 5: Study Drugs

Study Drug	Ocriplasmin 0.0625mg		Ocriplasmin 0.125mg		Sham
Study Drug Components	ocriplasmin 0.5mg/0.2mL	Sodium chloride (NaCl) 9mg/mL (0.9%)	ocriplasmin 0.5mg/0.2mL	Sodium chloride (NaCl) 9mg/mL (0.9%)	-
Formulation	Active Substance ocriplasmin 0.5mg/0.2mL Excipients Mannitol Citric acid Sodium hydroxide (NaOH) for pH adjustment Water for injection	NaCl 9mg/mL (0.9%)	Active Substance ocriplasmin 0.5mg/0.2mL Excipients Mannitol Citric acid Sodium hydroxide (NaOH) for pH adjustment Water for injection	NaCl 9mg/mL (0.9%)	-
Presentation	Clear and colourless solution	Clear and colourless solution	Clear and colourless solution	Clear and colourless solution	-
Volume for dilution	0.2mL	0.6mL	0.2mL	0.2mL	-
Volume to be administered	0.1mL		0.1mL		-

Table 5: Study Drugs (Continued)

Study Drug	Ocriplasmin 0.0625mg	Ocriplasmin 0.125mg	Sham
Route of Administration	Intravitreal injection	Intravitreal injection	Sham injection
Dosing Schedule	
 Up to 3 injections for subjects in the ocriplasmin 0.0625mg arm, administered at Day 0, Day 35 and Day 70 	
 Up to 3 injections for subjects in the ocriplasmin 0.125mg arm, administered at Day 0, Day 35 and Day 70^a 	
 3 sham injections for subjects in the sham arm, administered at Day 0, Day 35 and Day 70 Up to 2 sham injections for subjects in the ocriplasmin arms, administered at Day 35 and / or Day 70^a

^a All subjects assigned to the ocriplasmin arms will receive an intravitreal injection of ocriplasmin 0.0625mg or 0.125mg at Day 0. These subjects will be re-treated with the same dose of ocriplasmin at Day 35 and at Day 70 if, at that time, they do not have total PVD on both B-scan ultrasound and SD-OCT, as assessed by the masked B-scan expert reader and the masked CRC, respectively. Subjects who have total PVD on both B scan ultrasound and SD-OCT will receive subsequent sham injection(s) in place of ocriplasmin injection(s)

Ocriplasmin is supplied in a single use, glass (type I glass) vial containing 0.5mg ocriplasmin in 0.2mL solution (2.5mg/mL). Ocriplasmin vials are packed in carton boxes, each of which contains a single vial. Vials are closed with a chlorobutyl rubber stopper and a polypropylene flip-off cap.

NaCl (0.9%) is supplied in a single use ampoule containing 5mL NaCl 9mg/mL (0.9%).

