8.2.1. Adverse Events

All AEs must be recorded from the time of providing consent until the end of the study for all subjects.

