- ^l Randomisation can only occur after confirmation of eligibility by the B-scan expert reader, the CRC and the central laboratory
- ^m Post-injection IOP measurement and indirect ophthalmic examination will be performed by the unmasked treating investigator as many times as needed at his / her discretion but at least once within 60 minutes after the injection to exclude central retinal artery non-perfusion or other complications

Table 7: Study Visit Intervals

Interval	Optimal Interval	Allowed Interval
Visit 1 (Screening) → Visit 2 (Day 0)	10-14 days	10-17 days
Visit 2 → Post-injection Phone Call	24–48 hours	24–72 hours ^a
Visit 2 (Day 0) → Visit 3 (Day 7)	7 days	7±3 days (4–10 days)
Visit 2 (Day 0) → Visit 4a (Day 28)	28 days	28±3 days (25-31 days)
Visit 4a (Day 28) → Visit 4b (Day 35)	7 days	6-10 days
Visit 4b (Day 35) → Post-injection Phone Call	24–48 hours	24–72 hours ^a
Visit 4b (Day 35) → Visit 5 (Day 42)	7 days	7±3 days (4–10 days)
Visit 4b (Day 35) → Visit 6a (Day 63)	28 days	28±3days (25-31 days)
Visit 6a (Day 63) → Visit 6b (Day 70)	7 days	6-10 days
Visit 6b (Day 70) → Post-injection Phone Call	24–48 hours	24–72 hours ^a
Visit 6b (Day 70) → Visit 7 (Day 77)	7 days	7±3 days (4–10 days)
Visit 6b (Day 70) → Visit 8 (Day 98)	28 days	28±3days (25-31 days)
Visit 2 (Day 0) → Visit 9 (Month 9)	270 days	270±14 days (256-284 days)
Visit 2 (Day 0) → Visit 10 (Month 15)	450 days	450±14 days (436-464 days)
Visit 2 (Day 0) → Visit 11 (Month 24)	720 days	720±14 days (706-734 days)

^a If an unscheduled post-injection visit falls within the allowed interval for the 7-days post-injection visit (4-10 days after injection), the unscheduled post-injection visit and the Day 7 visit will take place on the same day

Table 8: Responsibilities Masked and Unmasked Study Staff and Need for Certification

Study Procedure	Masked Study Staff	Unmasked Study Staff	Certification needed
Study drug:			
Study drug accountability		X	
Injection-related procedures:			
IXRS access		X	
(Pre-)injection procedures		X	
1-hour post-injection assessment		X	
Scripted phone call 24-72 hours after the injection	X		
Conduct unscheduled study visit(s)	X		
Assess list of events that lead to withdrawal from repeat injection	X		
AE reporting:			
AEs during 1-hour post-injection assessment		X	
All other AEs	X		
Ophthalmic assessment:			
BCVA	X		
Colour vision (Roth 28-hue)	X		
B-scan ultrasound	X		X
Full ophthalmic examination	X		
7-standard field stereo colour fundus photography	X		X

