3. Conventions for Analysis and Computations

All Treated Subjects Analysis Set

A single analysis set will be used. The All Treated Subjects analysis set will include subjects who are randomized and receive the first injection of study treatment. Subjects will be assigned to the treatment they receive at the time of the first injection.

Baseline Value

Baseline value is defined as the last non-missing value prior to administration of the first injection of the study drug.

Change from Baseline

Change from Baseline is calculated as the difference between the value at a considered visit minus the Baseline value. Change from Baseline will be missing if either one of the Baseline Value or the value at the considered visit is missing.

Adverse Events

Adverse events are coded using MedDRA version 18.1.

If a subject has multiple occurrences of an AE after an injection, the subject is presented only once in the respective subject count. Events are counted each time in the event column. Ocular adverse events are those that occur in either eye. Events recorded as OU (both eyes) are counted once for the study eye and once for the non-study eye, and are counted as 2 separate ocular events.

Drug related events are events considered by the Investigator with a reasonable possibility that the study treatment caused the event or events with a missing relationship.

Where severity is missing, the adverse event will be assigned to the ‘severe’ category.

AEs will be attributed to the closest injection prior to the occurrence of the event. AEs with a start date corresponding to the date of one of the injections will be attributed to that particular injection.

Treatment Emergent Adverse Events

Treatment Emergent Adverse Events are adverse events with a start date on or post the date of the first injection, or a missing start date.

Concomittant Interventions/Anti-VEGFs

Concomittant Interventions (including Anti-VEGFs) are interventions with a start date on or post the date of the first injection, or a missing start date.

Imputation of Partially Missing Dates

The conventions for imputing partially missing dates are provided in the appendix of this document.

Age Computation

The Date of Birth (DOB) will be imputed to 01JULYYYY where YYYY correspond to the year of birth. The following SAS code will be used for calculating age.

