$$\text{floor}(\text{intck}(\text{'month'}, \text{DOB}, \text{first injection date}) - (\text{day}(\text{first injection date}) < \text{day}(\text{DOB}))) / 12$$

By Visit Layout

In tables summarizing data ‘By Visit’, post-injection 2 and 3 visits will be presented on 2 rows. The first row will be labelled ‘Day/Month xx, Post-Injection 2/3’ and will present data of subjects with 2 or 3 injections, respectively. The second row will be labelled ‘Day/Month xx, Missing Repeat Injection(s)’ and will present data of subjects who did not receive the complete set of repeat injections.

Early Termination Visit

The Early Termination visit corresponds to the last visit attended by subjects who discontinue from the study. Early Termination visits will be re-coded when possible. The related data will be summarized in the corresponding re-coded visit and in a visit named ‘*Early Termination*’. For example, if a subject discontinues with its last visit being the Day 28 visit, then the corresponding data will appear in the line ‘*Day 28, Post-Injection 1*’ and in the line ‘*Early Termination*’ of the summary tables.

Unscheduled Visit

Unscheduled visits will not appear in the summary tables, but in the listings.

Summary Statistics

Descriptive statistics for continuous variables and calculated change from baseline variables will include:

- number of subjects with available data
- mean and standard deviation
- median
- minimum and maximum

- 95% CI for mean, where indicated.

Categorical data and shift from baseline will be summarized by presenting:

- count
- percentage (where the denominator is based on the total number of subjects in the treatment group or overall, unless otherwise stated in the table footnotes)
- 95% CI for the proportion (Clopper-Pearson method), where indicated.

Protocol Deviations

Deviations from the protocol will be documented on an ongoing basis by the study monitors and project managers throughout the study. Protocol deviations are recorded outside the clinical database and will be reviewed by ThromboGenics during the course of the study, prior to database lock.

Missing Data

Missing data will not be replaced (unless otherwise specified), and data analysis will be performed based on the observed cases (OC) principle.

Subgroup Analysis

No subgroup analyses, nor analysis per center, will be performed.

Sensitivity Analysis

No sensitivity analyses will be performed.

Changes in Planned Analyses from the Protocol

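### Per-injection AE counts rest on windows of 35, 35 and 650 days and, in the ocriplasmin arms, pool ocriplasmin with substitute sham, so they cannot be compared across injections within an arm

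*SAP*

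**What the plan says.** SAP section 3, Adverse Events, sets the rule: "AEs will be attributed to the closest injection prior to the occurrence of the event". An event on an injection date goes to that injection. The same paragraph counts a subject once for repeated occurrences of an AE after an injection, so per-injection counts are intended. The definition of treatment-emergent events gives a start point but no end point.

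SAP section 3, All Treated Subjects Analysis Set, fixes the arm: "Subjects will be assigned to the treatment they receive at the time of the first injection". By Visit Layout splits the later visits by number of injections; the first row "will present data of subjects with 2 or 3 injections, respectively". Under Summary Statistics the default percentage denominator is the whole treatment group, unless a table footnote says otherwise.

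Protocol 6.1, Table 5 allows "Up to 2 sham injections for subjects in the ocriplasmin arms, administered at Day 35 and / or Day 70". These go to subjects who have total PVD on both imaging methods (Protocol 3.2). A sham does not penetrate the globe (Protocol 3.6.1). The control arm follows the same calendar: "Subjects assigned to the sham arm will receive 3 sham injections at Day 0, Day 35 and Day 70". On collection, Protocol 8.2.1 says: "All AEs must be recorded from the time of providing consent until the end of the study for all subjects". Subjects withdrawn from repeat injection stay in follow-up to the end of the study (Protocol 4.2.1).

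**The concern.** Protocol 1.5 describes this as the first study of up to three ocriplasmin injections in moderate to very severe NPDR, and Protocol 3.4 names inflammation after a second or third injection for escalation to the DMC. Readers will therefore look at per-injection AE counts to judge repeat dosing.

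Two features of the rule get in the way. First, the last injection collects everything to Month 24, so its count is mostly a count of follow-up time. Second, a count after injection 2 or 3 in an ocriplasmin arm includes subjects who received neither drug nor a penetrating procedure at that injection. The first feature makes injection 3 look worse than injection 1 with no drug effect; the second pulls a true repeat-dose effect towards zero.

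**Working it through.** The plan states no window lengths, so they are derived here from its schedule.

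**1. Nominal windows** (injection days from Protocol 3.2; last visit at Day 720 from Table 7)
- Injection 1: 35 − 0 = 35 days
- Injection 2: 70 − 35 = 35 days
- Injection 3: 720 − 70 = 650 days
- Ratio 650/35 = 18.6; share of follow-up 650/720 = 90.3%

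**2. Windows within the Table 7 limits**
- Each injection-to-injection interval is 25 to 31 days plus 6 to 10 days, that is 31 to 41 days.
- The third injection then falls between Day 62 and Day 82, and the last visit between Day 706 and Day 734.
- Third window: 706 − 82 = 624 to 734 − 62 = 672 days.
- Ratio: 624/41 = 15.2 to 672/31 = 21.7.

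**3. Subjects withdrawn from repeat injection.** Their last window runs to Month 24: up to 720 days after injection 1, or 720 − 35 = 685 days after injection 2. The injection 1 and 2 counts are therefore not uniformly 35-day counts either.

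**4. Effect of window length alone.** Assume a constant background rate r, the same in every window and unrelated to drug. The share with at least one event in d days is 1 − exp(−r·d/365.25). The documents give no rate; 0.2 and 0.5 per subject-year are assumptions.

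| r per year | 35 days | 650 days | 28 days |
|---|---|---|---|
| 0.2 | 1.9% | 30% | 1.5% |
| 0.5 | 4.7% | 59% | 3.8% |

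With a fixed 28-day window, the last column would apply to all three injections.

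**5. Share of substitute sham in the ocriplasmin arms.** The documents do not give it, so it is bracketed.
- Injection 2: about 13%, using the 13.4% total PVD rate at Day 28 after one 0.125mg injection (Protocol 1.4.2.2). That rate comes from the Phase 3 studies for the VMT indication, and VMT is an exclusion here.
- Injection 3, lower end: about 13%, if no first-injection failure responds later. In study TG-MV-004, 0 of 7 did after two further injections (Protocol 1.3.2).
- Injection 3, middle: 1 − (1 − 0.134)² = 25%, if failures respond again at the same rate.
- Injection 3, upper end: 40%, the planning rate by Month 3 (Protocol 9.1). It is cumulative over all three injections, so it is a ceiling. It would also cap injection 2 if every response came after the first injection.
- In planned subjects per arm: 46 × 0.134 = 6.2 and 46 × 0.40 = 18.4. With 48 randomised at 2:2:1, an ocriplasmin arm has about 48 × 2/5 = 19.2 subjects, giving about 2.6 and 7.7.

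**6. Dilution.** If ocriplasmin at a repeat injection raised AE risk by 10 points and substitute sham by none, the pooled excess would be 10 × (1 − 0.134) = 8.7 points at injection 2, and between 8.7 and 10 × (1 − 0.40) = 6.0 points at injection 3.

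**The case against.** The strongest reply is that the published SAP is abbreviated. Its section 1 says mock-up tables and listings, and some other information, were left out, and denominators may be set in footnotes. A column by product, or a denominator of subjects injected, may exist. This stands: the point can be made only against the published convention.

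A reader might infer that the per-injection tables cannot show the safety of repeat ocriplasmin at all. The documents do not support that:
- The sham arm has the same three-injection calendar, so arms compared at the same injection number have the same nominal windows.
- On the protocol's own PVD figures, most repeat injections in the ocriplasmin arms would still be ocriplasmin.
- Protocol 9.6.2 plans AE tables by onset from study treatment, and Protocol 9.6.1 plans letter loss of 15 or more from Day 0 to Day 7 after each injection. Neither is on the SAP's list of dropped analyses. However, the first states no window or product split, and the second does not cover AEs.
- The by-visit rows sit at fixed times after injection, so the window problem does not reach them; only the product mixing does.

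A split by product also has a cost. Product at injections 2 and 3 depends on PVD status after randomisation, so the split compares responders with non-responders, and a late effect of earlier ocriplasmin would be filed under sham. Classifying by first injection avoids this and agrees with the protocol's Safety Analysis Set. That supports keeping the arm-level table as the main one. It does not rescue comparison of injections 1, 2 and 3 within an arm.

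**Conclusion.** The point holds in a limited form. As published, the rule makes per-injection AE counts non-comparable across injections within an arm, because the third window is about 18.6 times the others (about 15 to 22 within the allowed visit limits). That size follows from the schedule alone, for subjects who receive all three injections; the event percentages rest on the assumed constant background rates.

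The product mixing is a second, smaller defect: about 13% sham at injection 2 and 13% to at most 40% at injection 3, which shrinks a true 10-point excess to about 8.7 and 6.0 to 8.7 points. These shares rest on PVD rates borrowed from another population or from the planning assumption.

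Comparison of whole arms remains valid, as does comparison of arms at the same injection number as far as nominal window length is concerned. Safety is descriptive with no testing, so the risk is misreading of a table rather than a wrong test.

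**What to change.** - Keep the arm-level AE table, by treatment at first injection, as the main safety comparison.
- Present per-injection AEs in one fixed window after each injection, for example 28 days, with later events in a separate follow-up column. A 28-day window fits inside the shortest allowed gap of 31 days. It also suits Protocol 1.5.1.1, which reports that most AEs after a single 0.125mg injection in VMT arose in the first week.
- Use the number of subjects given that injection as the denominator, and state it in the table.
- Add a supplementary split by product given (ocriplasmin dose or sham) at injections 2 and 3, and apply it to the post-injection 2 and 3 visit rows. Label it descriptive and not a randomised comparison.
- If the full SAP's mock-ups already do this, say so in the published version.

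The cost is SAP wording and one extra layout; treatment numbers for each injection already pass from IXRS to the eCRF (Protocol 3.5). Since SAP section 1 describes the final analysis as having taken place, this would now be a labelled supplementary tabulation or, at the least, a caveat in the study report. The downsides are small cells with 48 randomised, and the dependence of the product split on PVD response, including late effects of earlier ocriplasmin appearing under sham.

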3.4. Data Monitoring Committee

In order to maintain a general safety oversight and to monitor the risk / benefit balance, a DMC will be established for this study.

From the time the first subject is injected until the last subject completed the Month 3 visit (Visit 8), the following TEAEs will be escalated to the DMC on an ongoing basis:

- Lens subluxation
- Iso-electric ffERG

- Clinically significant increased intraocular inflammation after repeat (2nd or 3rd) injection
- BCVA decrease \geq 15 letters from baseline, without evidence of resolution or stabilisation within 24 hours
- Foveal detachment or worsening of a foveal detachment
- Any other event at the discretion of the Sponsor

The DMC will conduct periodic reviews at the following pre-defined timepoints:

- After approximately 20% of the subjects completed the Month 2 visit (Visit 6b)
- After approximately 50% of the subjects completed the Month 3 visit (Visit 8)
- After all subjects completed the Month 3 visit (Visit 8)
- After all subjects completed the Month 15 visit (Visit 10)

In addition, *ad hoc* DMC meetings may be organised.

The DMC will be empowered to make recommendations to the Sponsor on further study conduct. Such recommendations include continuing or terminating the study or modifications to the study. Another recommendation may be temporary suspension of enrolment and / or study treatment until some uncertainty is resolved.

The DMC responsibilities and procedures will be documented in the DMC Charter.

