8.4.1.2. Adverse Event Intensity

The unmasked treating investigator / masked Investigator shall assess and record the intensity of the (S)AE according to the following scale:

- Mild (awareness of sign or symptom, but easily tolerated)
- Moderate (discomfort sufficient to cause interference with normal activities)
- Severe (incapacitating, with inability to perform normal activities)

An AE that is assessed as 'Severe' should not be confused with an SAE. 'Severe' is part of a scale used for rating the intensity of an event. An event is defined as 'Serious' when it meets 1 of the pre-defined outcomes as described in [Section 8.3.2](#). A severe AE can be of relatively minor medical significance / non-serious (*e.g.* severe itching). Similarly, an SAE can be of mild intensity (*e.g.* mild chest pain).

For AEs that change in intensity, the start and stop date of each intensity should be recorded.

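### The SAP sets treatment emergence and injection attribution by AE start date, with no worsening clause and no rule linking the separately dated intensities of one AE

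*SAP*

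**What the plan says.** SAP section 3, in its paragraph on treatment emergence, defines TEAEs as "adverse events with a start date on or post the date of the first injection"; undated AEs qualify as well. That is the whole definition. Worsening is not mentioned, and the protocol has no TEAE definition of its own to fall back on.

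Under Adverse Events, the same section sets attribution ("AEs will be attributed to the closest injection prior to the occurrence of the event"), with a same-day rule ("AEs with a start date corresponding to the date of one of the injections will be attributed to that particular injection"). Its rule for counting subjects reads: "If a subject has multiple occurrences of an AE after an injection, the subject is presented only once in the respective subject count". Its separate rule for event totals, which does not say how intensity periods are handled, reads: "Events are counted each time in the event column".

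On data collection, protocol section 8.4.1.2 requires: "For AEs that change in intensity, the start and stop date of each intensity should be recorded". Section 8.4.1 also asks for one onset date and one resolution date per AE. Section 8.2.1 starts AE recording at consent, and Table 7 allows 10–17 days from screening to Day 0, so AEs can begin before any injection.

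These rules feed the proportion of subjects with an ocular TEAE in the study eye (protocol 9.6.1). They also feed the subject and event counts and the tables by maximum severity and by onset relative to treatment (9.6.2).

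**The concern.** One AE can carry several dates: its onset and the start of each later intensity. The SAP relies on a start date without saying which, and has no rule for joining the intensity periods of one AE. A rule based only on onset cannot see worsening after an injection. A rule applied to each intensity period cannot tell worsening from recovery.

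This matters because ocular TEAEs in the study eye are the principal safety endpoint and because repeat injection is the less familiar exposure: protocol section 1.3.2 reports only 9 subjects with multiple 0.125mg injections in the earlier Phase 2 study. The protocol also treats change after a later injection as informative. Its list for escalation to the DMC (section 3.4) includes "Clinically significant increased intraocular inflammation after repeat (2nd or 3rd) injection" and worsening of a foveal detachment.

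**Working it through.** The plan gives no figure to reproduce. The check applies the SAP rules literally to invented AE histories, with injections on Days 0, 35 and 70.

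**Readings compared**

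- *Onset reading:* one record per AE, dated by first onset s. TEAE if s ≥ 0; attributed to the latest injection day not after s.
- *Per-intensity reading:* one record per intensity period, with the same rules applied to each period's start.
- *Linked rule (the proposal below):* one event per AE. It is a TEAE if onset ≥ 0, or if intensity on or after Day 0 exceeds its pre-dose maximum. A rise above the earlier maximum after a later injection is flagged there without adding an event.

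**TEAE events, with the injection charged in brackets**

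| History | Onset | Per intensity | Linked |
|---|---|---|---|
| A: mild from Day −7, severe from Day 3 | 0 | 1 (inj. 1) | 1 (inj. 1, by worsening) |
| B: severe from Day −7, mild from Day 3 | 0 | 1 (inj. 1) | 0 |
| C: mild from Day 5, severe from Day 37 | 1 (inj. 1) | 2 (inj. 1, inj. 2) | 1 (inj. 1, flagged under inj. 2) |
| D: severe from Day 5, moderate from Day 20, mild from Day 40 | 1 (inj. 1) | 3 (inj. 1, 1, 2) | 1 (inj. 1) |
| Sum | 2 | 7 | 3 |

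The onset reading misses A and leaves C's worsening under injection 1. The per-intensity reading catches both, but makes B a TEAE because it improved and counts D three times, once under injection 2. The sums reflect the histories chosen and are not rates. History C presumes an AE that does not itself bar repeat injection under protocol section 4.2.1, such as floaters.

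**What can reach the principal proportion.** It counts subjects with any ocular study-eye TEAE, so attribution and event counts cannot move it. Only cases like A or B can, and only in a subject with no other ocular study-eye TEAE.

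**Size per such subject.** The protocol's clarification note gives 48 randomised, with planned allocation 2:2:1. The published text gives no actual arm sizes, so expected ones are used.

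- Sham: 48 × 1/5 = 9.6; 1/9.6 = 10.4 points.
- Each ocriplasmin arm: 48 × 2/5 = 19.2; 1/19.2 = 5.2 points.

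These are maxima. In the pooled diabetic retinopathy data (protocol 1.3.2), 37 of 62 subjects given 0.125mg (59.7%) had an ocular study-eye TEAE, so 25/62 = 40.3% had none. Assume that rate carries over and that misclassification is independent of having another TEAE. The average shift per misclassified subject in the 0.125mg arm is then 5.2 × 0.403 = 2.1 points.

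**Exposure at later injections.** Protocol section 1.5.1.1 says AEs after a single 0.125mg injection mostly began in the first week and mostly resolved within 2–3 weeks. An AE starting by Day 7 and lasting 21 days ends by Day 28. Injection 2 is planned for Day 35; the earliest day Table 7 allows is 25 + 6 = Day 31. Most such AEs would be over by then.

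**The case against.** The strongest case against has five parts.

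1. *Inflammation.* A reader might infer that the final tables would place the DMC's inflammation signal under the earlier injection. The documents do not support that. Section 4.2.1 withholds or postpones repeat injection when intraocular inflammation is active, so inflammation after injection 2 or 3 would normally be a new onset, which the SAP attributes correctly. DMC escalation also runs during the study, with AEs entered within 24 hours, and does not depend on this SAP. This objection stands. The attribution gap is left with ongoing AEs that do not bar re-injection.

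2. *Storage.* A reader might infer that event counts are inflated. That holds only if each intensity is a separate AE record, and no passage says so. The single onset date and the advice to record one comprehensive event per pathology (8.4.1), together with the maximum-severity table (9.6.2), fit one record per AE better. This stands too, but the reading it favours is the one that misses worsening.

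3. *Pre-existing conditions.* Protocol section 8.3.3 makes worsening of a condition present or detected at the start of the study an AE in its own right. If recorded with its own date, it is captured. That narrows the missed-TEAE case mainly to AEs arising between consent and Day 0. It does not settle attribution to injections 2 and 3.

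4. *Abbreviated SAP.* Mock-up tables and some other content are left out, so a footnote may hold the rule. That cannot be excluded. However, the published section 3 gives comparably detailed conventions for bilateral events, missing severity and same-day onset, and this rule belongs beside them.

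5. *Convention.* Whether history C is one event with a flag or two events is a choice. Agreed, but the SAP has to make it.

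**Conclusion.** The point holds as a gap in the stated rule. Read as onset, the start-date rule omits a pre-dose AE that worsens after injection 1 and leaves later worsening of an ongoing AE under the earlier injection. Read per intensity, it can turn recovery into a new event or TEAE. The two sets of errors are alternatives, because the documents do not say how intensity changes are stored.

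The effect is probably small. The pre-dose window is usually 10–17 days, and few AEs should span a repeat injection if the earlier single-injection experience carries over. The 10- and 5-point figures should not be read as an expected bias: each is the most that one misclassified subject can move an arm, and only if that subject has no other ocular study-eye TEAE. The attribution and count problems are confined to event-count and by-injection summaries. Safety is descriptive, without testing. The number of affected subjects cannot be computed, since no AE data are given. The change is still worth making because it corrects the definition behind the principal safety endpoint with dates already collected. Confidence is moderate, mainly because a rule may exist in the unpublished part of the SAP.

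**What to change.** In SAP section 3, keep the existing treatment of missing start dates and the same-day attribution rule, and add:

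- Start date means AE onset.
- Intensity periods of one AE are linked and counted as one event at its maximum intensity.
- An AE with onset before the first injection is also treatment-emergent if its intensity on or after that injection exceeds its maximum before it. It is attributed to the injection that the rise follows.
- An AE ongoing at a repeat injection whose intensity then exceeds its earlier maximum is also flagged under that injection as worsened, without adding to the overall event count.
- A decrease in intensity does not create an event.

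SAP section 1 says the final analysis has taken place. The practical step is therefore to state in the study report which date and linking rule were used, and to rerun the AE tables if they differ from the above. If the full SAP or its table footnotes already contain such a rule, quoting it closes the point.

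The cost is a few sentences and a short program on intensity dates that the protocol already requires. The one drawback is that a worsened AE appears in two by-injection columns, which needs a footnote.
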